### 10.4 Definition of a Serious Adverse Event (SAE)

**Serious Adverse Event (SAE)** is any untoward medical occurrence at any dose that:

- results in death
- is life-threatening (defined as an event in which the subject was at risk of death at the time of the event; it does not refer to an event which hypothetically might have caused death if it were more severe)
- requires inpatient hospitalization or causes prolongation of existing hospitalization (see **NOTE\***: below for exceptions)
- results in persistent or significant disability/incapacity
- is a congenital anomaly/birth defect
- is an important medical event, defined as a medical event that may not be immediately life-threatening or result in death or hospitalization but, based on appropriate medical and scientific

judgment, may jeopardize the subject or may require intervention (e.g., medical, surgical) to prevent one of the other serious outcomes listed above. Examples of such events include but are not limited to intensive treatment in an emergency department or at home for allergic bronchospasm; blood dyscrasias or convulsions that do not result in hospitalization.

- Potential drug-induced liver injury (DILI) is also considered an important medical event-- see the DILI section below for a definition of a potential DILI event.

Suspected transmission of an infectious agent (eg, pathogenic or non-pathogenic) via the study drug is an SAE.

Although pregnancy, overdose, and cancer are not always serious by regulatory definition, these events must be handled as SAEs

*\*NOTE: The following hospitalizations are not considered SAEs:*

- A visit to the emergency room or other hospital department lasting less than 24 hours that does not result in admission (unless considered an “important medical event” or a life-threatening event)
- Elective surgery planned before signing consent
- Admissions as per protocol for a planned medical/surgical procedure
- Routine health assessment requiring admission for baseline/trending of health status (eg, routine colonoscopy)
- Medical/surgical admission other than remedying ill health state that was planned before study entry. Appropriate documentation is required in these cases
- Admission encountered for another life circumstance that carries no bearing on health status and requires no medical/surgical intervention (eg, lack of housing, economic inadequacy, caregiver respite, family circumstances, administrative reason)

#### **10.4.1 Serious Adverse Event Collecting and Reporting**

Following the subject’s written consent to participate in the study, all SAEs, whether related or not related to study drug, must be collected, including those thought to be associated with protocol-specified procedures. All SAEs must be collected that occur during the screening period and within 30 days of discontinuing dosing. If applicable, SAEs must be collected that relate to any later protocol-specific procedure (such as follow-up skin biopsy).

The investigator should report any SAE occurring after these time periods that is believed to be related to study drug or protocol-specified procedure.

An SAE report should be completed for any event where doubt exists regarding its status of seriousness.

If the investigator believes that an SAE is not related to study drug, but is potentially related to the conditions of the study (such as withdrawal of previous therapy, or a complication of a study procedure), the relationship should be specified in the narrative section of the SAE Report Form.

SAEs, whether related or unrelated to the study drug, and pregnancies must be reported to BMS within 24 hours. SAEs must be recorded on the SAE Report Form; Pregnancies on a Pregnancy Surveillance Form.

**SAE Email Address:** [contact]

**SAE [contact]

If only limited information is initially available, follow-up reports are required. (Note: Follow-up SAE reports should include the same investigator term(s) initially reported.)

If an ongoing SAE changes in its intensity or relationship to study drug or if new information becomes available, a follow-up SAE report should be sent within 24 hours to the BMS (or designee) using the same procedure used for transmitting the initial SAE report.

All SAEs should be followed to resolution or stabilization.

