## 5.4 End of Study

A final visit will be conducted at day 180 in person. Study medication will be collected at this visit and the patient will be started on standard of care therapy. Decisions regarding anticoagulation will be based off the subject's individual needs as assessed by the Principal Investigator or Sub-Investigator.

30 days after the EOS a phone call will be made to assess for AE's or SAE's that may have occurred during that time frame.

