## 5.7 Subject Completion/Early Withdrawal

It will be documented whether or not each subject completed the clinical study. A subject is considered to have completed the study if he/she has taken all study medications for 6 months and has completed 6 month study assessments or withdrew from the study due to the occurrence of a recurrent embolic stroke, hemorrhagic transformation or death. If a subject does not complete the treatment phase, their data will be used for efficacy and for any safety analysis.

It is understood that withdrawals may occur during a trial. Each subject has the right to withdraw from the trial at any time for any reason without affecting the right to treatment by the investigator. Subjects who do not complete the treatment phase for other reasons then mentioned above, should be followed at day 14 and EOS visits, if possible. At minimum these patients should have a monthly phone call to assess AE/SAE and vital status if they are unable to continue follow-up in clinic.

Subjects needing to withdraw prior to the completion of the study and who do not agree to continue in follow-up should return to the clinic for completion of early withdrawal procedures, as outlined in table 1.

Reasons that a subject may discontinue the study include the following:

- Adverse events including recurrent stroke or hemorrhagic transformation
- Intercurrent illnesses
- Any significant new medical condition
- Protocol violation
- Non-compliance to study medication regimen

- Use of any investigational drug other than the study medication
- Intake of prohibited medication
- Pregnancy
- Subject withdrew consent or lost to follow-up
- Other (reason to be documented)

Withdrawals due to intercurrent illnesses or AEs will be fully documented in the CRF with the addition of supplementary information if available and/or appropriate. Withdrawals due to non-attendance will be followed-up by the investigator to obtain the reason for non-attendance.

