#### **6.6 Early Withdrawal (EW)**

- Physical exam
- Vital Signs
- Collect Laboratory assessments including INR for Warfarin arm
- Urine pregnancy test if required
- MRI or CT scan
- ECG
- NIHSS ,mRS and SS-QOL
- Assess Drug Compliance
- Provide patient education
- Assess concomitant medication /procedure changes
- Assess AE/SAE's
- Start on non-study Anticoagulation therapy

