### 10.5 IRB/IEC Notification of SAEs

The investigator will promptly notify the IRB of all SAEs and other unanticipated problems related to research using the applicable IRB reporting form(s). External SAEs that are unexpected and related to the study intervention will be reported as they are received, within 24 hours of receipt, using the External SAE form (if applicable).

**All Serious Adverse Events (SAEs) that occur following the subject's written consent to participate in the study through 30 days of discontinuation of dosing must be reported to BMS Worldwide Safety.**

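### The schedule's windows allow the final AE/SAE call as early as 10 days after end of study, although SAEs must be collected for 30 days after dosing stops; patients who decline follow-up after early withdrawal have no scheduled contact at all

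*Combined protocol and SAP*

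**What the plan says.** **The collection duty.** Section 10.4.1: "All SAEs must be collected that occur during the screening period and within 30 days of discontinuing dosing". Section 10.5 repeats it as a reporting duty: SAEs from consent "through 30 days of discontinuation of dosing must be reported to BMS Worldwide Safety".

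**The last call, in the text.** Section 5.4 counts the call from the EOS visit: "30 days after the EOS a phone call will be made to assess for AE's or SAE's that may have occurred during that time frame". It gives no window. The same section fixes the end of study drug: "Study medication will be collected at this visit and the patient will be started on standard of care therapy".

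**The last call, in the table.** The Schedule of Study Procedures puts EOS (Visit 9) at day 180 (±10) and the 30-day phone call (Visit 10) at day 210 (±10). Its footnote makes the day of the event the origin for study days. AE/SAE recording is ticked at the call, and nothing follows it.

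**Early stops.** For patients who stop treatment for reasons other than recurrent embolic stroke, hemorrhagic transformation or death, section 5.7 says they "should be followed at day 14 and EOS visits, if possible", and adds: "At minimum these patients should have a monthly phone call to assess AE/SAE and vital status if they are unable to continue follow-up in clinic". Section 7.5.2 requires monthly phone or clinic contact to the end of the study under its rules for suspending dosing. Subjects "who do not agree to continue in follow-up should return to the clinic for completion of early withdrawal procedures, as outlined in table 1". Neither section 6.6 nor the EW column lists any contact after that visit. The last item in 6.6 is "Start on non-study Anticoagulation therapy".

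**The concern.** The table and the text count the same call from different origins. Section 5.4 follows the actual EOS visit. The table follows the index event and gives each visit its own ±10 days, so a late EOS visit and an early call are both in window while the interval between them shrinks. A site that looks for a window finds one only in the table.

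This call is the last planned occasion on which anyone asks about adverse events. SAEs after an early call reach the database only if someone reports them spontaneously. The days affected come just after study drug is stopped and other anticoagulation begins, in a trial whose main outcomes are recurrent stroke and intracranial bleeding. If the number of days asked about differs between patients, a count of SAEs through 30 days after dosing is not equally complete for all of them.

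The early-withdrawal gap is a separate matter. The duty in 10.4.1 and 10.5 makes no exception for these patients, yet the plan schedules no inquiry after the EW visit for those who decline follow-up.

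**Working it through.** **Inputs.** SAE period: 30 days after the last dose (10.4.1, 10.5). EOS: day 180 ± 10, so days 170 to 190 (schedule). Call: day 210 ± 10, so days 200 to 220 (schedule). Last dose taken to be at about EOS, because study drug is collected then (5.4).

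**Step 1. The plan's own interval.** 210 − 180 = 30 days. The nominal days agree with 5.4.

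**Step 2. Range allowed by the table.** Gap = call day − EOS day.
- Minimum: (210 − 10) − (180 + 10) = 200 − 190 = 10 days.
- Maximum: (210 + 10) − (180 − 10) = 220 − 170 = 50 days.

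| EOS on day | Gap allowed by the table | Largest shortfall from 30 days |
|---|---|---|
| 170 | 30 to 50 days | 0 |
| 180 | 20 to 40 days | 10 |
| 190 | 10 to 30 days | 20 |

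**Step 3. How often the call would be early (illustration).** Assume that every whole day in each window is equally likely and that the two visits are independent. There are 21 × 21 = 441 day pairs.
- A shortfall of k days (k = 1 to 20) arises in 21 − k pairs. The total is 20 + 19 + … + 1 = 210 pairs, and 210/441 = 47.6% of calls come before day 30.
- A gap of 20 days or less (k = 10 to 20) arises in 11 + 10 + … + 1 = 66 pairs, and 66/441 = 15.0%.
- Total shortfall: Σ k(21 − k) = 21 × 210 − 2,870 = 1,540 days. The mean is 1,540/210 = 7.3 days among early calls and 1,540/441 = 3.5 days over all calls.

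**Step 4. Under section 5.4 as worded.** The gap is 30 days for any EOS day. With EOS on days 170 to 190 the call falls on days 200 to 220, which is exactly the table's window. If ±10 days were placed around EOS + 30 (an assumption, since 5.4 gives no window), the gap would be 20 to 40 days and up to 10 days would still be unasked. Only a window with no early side covers the period for everyone.

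**Step 5. Who has contact after stopping early.**

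| Patient | Scheduled contact afterwards | Source |
|---|---|---|
| Stops treatment, stays in follow-up | Day 14 and EOS visits if possible; monthly call if unable to attend clinic | 5.7 |
| Dosing suspended for safety | Monthly phone or clinic contact to end of study | 7.5.2 |
| Leaves after recurrent embolic stroke | Not clearly covered: counted as having completed, and the follow-up rule addresses other reasons | 5.7 |
| Withdraws and declines follow-up | None after the EW visit | 5.7, 6.6, schedule |

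In the last row the unasked time is the full 30 days if the last dose is at the EW visit, and less if dosing stopped earlier.

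**The case against.** The strongest reply is that section 5.4 already ties the call to the EOS visit. By Step 4, a site that follows 5.4 is always inside the table's window, so table and text can be met together, and a call on day 200 after EOS on day 190 would breach 5.4. This stands in part. A reader might infer from the table that the call is simply fixed at day 210, and the documents do not support that. But nothing says which of the two governs, only the table states a tolerance, and a call 10 days after EOS would be in window by the table.

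A reader might also infer that early withdrawals as a group get no call, or that this is what produces the 10-day figure. Neither follows. Sections 5.7 and 7.5.2 provide continued visits or monthly contact for those who stay in follow-up or are suspended for safety. The 10 days come from the two visit windows alone. Patients who refuse follow-up may also refuse a call, which limits what any schedule can achieve.

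The duty to collect SAEs does not lapse with an early call. Section 10.4.1 also asks for later events thought to be related, and section 10.12 gives subjects a study doctor on call for emergencies. That stands: the weakness is in scheduled inquiry, not in the collection rule.

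Finally, the documents do not show that patients who decline follow-up are at highest risk, and they give no rate for them. The only allowance is up to 125 subjects for 120, that is 5/125 = 4%, for drop-outs and screen failures together.

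**Conclusion.** The point holds as two separate gaps in safety ascertainment.

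1. The schedule conflicts with 5.4 and with 10.4.1 and 10.5. By the table, the last inquiry can come 10 to 50 days after EOS, leaving up to 20 of the 30 days unasked. The range follows from the stated windows and rests only on the last dose being at about EOS. The share of early calls (47.6%) and the mean shortfall (3.5 days over all calls) also rest on the equal-likelihood assumption and ignore 5.4, so they illustrate and do not predict.
2. Patients who decline follow-up have no scheduled contact after the EW visit, and cover for those leaving after a recurrent embolic stroke is unclear. The shortfall is up to 30 days per patient. The number of such patients cannot be derived from the documents.

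The planned outcome analyses are untouched: primary endpoint data end at 180 days (7.1) and intracranial hemorrhage is analysed at 30 and 180 days (8.1.3), both before the call. The correction is still worth making, because it costs almost nothing and there is no later contact to recover a missed event.

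**What to change.** - **Schedule and 5.4.** Count Visit 10 from the last dose of study drug, with no early side to the window, for example a call 30 to 40 days after the last dose. Drop the fixed day 210 (±10): with EOS on day 190 the call would fall on days 220 to 230. Use the same wording in the table, 5.4 and 10.4.1.
- **EW column and 6.6.** Add one such call, and ask for the patient's agreement to it at the EW visit even if all other follow-up is declined. Record refusals, so that the report can say for how many patients the 30 days were not covered.
- **Section 5.7.** State what contact applies to patients who leave after a recurrent embolic stroke. For those who stop drug early but stay in follow-up, state that the existing visits or monthly contact serve this purpose and whether the call after EOS is kept.

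Cost: the call window narrows from 21 days to 11, and each consenting early withdrawal needs one short call. There are no new visits or procedures and no effect on sample size or the primary analysis.

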#### 10.4.2 Relationship of SAE to study drug or other intervention

##### Assessment of Severity

The severity of each SAE will be assessed as described in the following table:

##### *Assessment Definition*

1 = Mild: Discomfort noted, but no disruption of normal daily activities; slightly bothersome; relieved with or without symptomatic treatment

2 = Moderate: Discomfort sufficient to reduce or affect normal daily activity to some degree; bothersome; interferes with activities, only partially relieved with symptomatic treatment

3 = Severe: Discomfort sufficient to reduce or affect normal daily activity considerably; prevents regular activities; not relieved with symptomatic treatment

For each solicited symptom, the subject will be asked if they sought medical advice (i.e. contact with a member of medical personnel) for this symptom.

##### Assessment of Causality

The investigator will attempt to explain each SAE and assess its causal relationship, if any, to the Study Medication . The degree of certainty with which an SAE can be attributed to Study Medication (or alternative causes, e.g. natural history of the underlying diseases, concomitant therapy, etc.) will be determined by how well the event can be understood in terms of one or more of the following:

- Reaction of similar nature having previously been observed with this type of medication.
- The event having often been reported in literature for similar types of medication.

The investigator will assess causality of all AEs, using the following method:

In your opinion, is there a reasonable possibility that the AE may have been caused by the study medication?

- No.
  - **Unrelated:** there is no suspicion that there is a relationship between Study Medication and AE, there are other more likely causes and the Study Medication is not suspected to have contributed to the AE.
- Yes.
  - **Related:** there is suspicion of a relationship between the study medication and AE (without determining the extent of probability); there are no other more likely causes and study medication is suspected to have contributed to the AE.

Events considered related to the study medication will be further classified as follows:

**Probable**-- AE cannot be reasonably explained by other factors (i.e. clinical condition, environmental/toxic factors or other treatments)

**Possible**-- AE can be reasonably explained by other factors (as mentioned above)

**Unlikely**-- AE occurs within an unusual time frame of administration of study medication and can also be reasonably explained by other factors (as mentioned above)

Non-serious and serious AEs will be evaluated as 2 distinct types of events given their different medical nature. If an event meets the criteria to be determined "serious", it will be examined by the investigator to the extent to be able to determine ALL contributing factors applicable to each SAE.

Other possible contributors include:

- Underlying disease
- Other medication
- Protocol required procedure
- Other cause (specify)

### 10.4.3 Definition of Severity

All AEs will be graded if possible by the Common Terminology Criteria for Adverse Events v4.03 (CTCAE). The severity of AEs that cannot be graded by CTCAE version 4.0 will be categorized as follows:

**Grade 1** – Transient or mild discomfort; no limitation in activity; no medical intervention/therapy required.

**Grade 2** – Mild to moderate limitation in activity, some assistance may be needed; no or minimal medical intervention/therapy required.

**Grade 3** – Marked limitation in activity, some assistance usually required; medical intervention/therapy required, hospitalizations possible.

**Grade 4** – Extreme limitation in activity, significant assistance required; significant medical intervention/therapy required hospitalization or hospice care probable.

**Grade 5** – Death.

### 10.5 IRB/IEC Notification of SAEs

The investigator will promptly notify the IRB of all SAEs and other unanticipated problems related to research using the applicable IRB reporting form(s). External SAEs that are unexpected and related to the study intervention will be reported as they are received, within 24 hours of receipt, using the External SAE form (if applicable).

**All Serious Adverse Events (SAEs) that occur following the subject's written consent to participate in the study through 30 days of discontinuation of dosing must be reported to BMS Worldwide Safety.**

#### 10.5.1 SAE Reconciliation

The investigator will reconcile the clinical database SAE cases transmitted to BMS Global Pharmacovigilance (GPV&E). Frequency of reconciliation will be every three months and once once prior to study database lock. BMS GPV&E will e-mail upon request from the investigator, the GPV&E reconciliation report. Requests for reconciliation should be sent to [[contact]](mailto:[contact]). The data elements listed on the GPV&E reconciliation report will be

used for case identification purposes. If the investigator determines a case was not transmitted to BMS GPV&E, the case will be sent immediately

#### **10.5.2 Follow-up report**

If an SAE has not resolved at the time of the initial report, a follow-up report including all relevant new or reassessed information (e.g., concomitant medication, medical history) will be submitted to the IRB. All SAE will be followed until either resolved or stable.

#### **10.5.3 Non-Serious Adverse Events**

A nonserious adverse event is an AE not classified as serious.

#### **10.5.4 Non-Serious Event Collecting and Reporting**

The collection of non-serious adverse event (NSAE) information should begin at initiation of study drug. Nonserious adverse event information should also be collected from the start of a placebo lead-in period or other observational period intended to establish a baseline status for the subjects.

Nonserious AEs should be followed to resolution or stabilization, or reported as SAEs if they become serious. Follow-up is also required for nonserious AEs that cause interruption or discontinuation of study drug, or those that are present at the end of study treatment as appropriate.

**Nonserious Adverse Events are provided to BMS via annual safety reports (if applicable), and interim or final study reports.**

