## Schedule of Study Procedures

TIA -Apixaban group	Screen/ Baseline	Treatment Initiation	Maintenance ‡						End of Study	30day PC	Early Withdrawal	Unsch
			3	4	5	6	7	8				
Visit Number	1	2	3	4	5	6	7	8	9	10		
Study Days (Visit Window)	0	$\beta$ (See also table 2)	14 ( $\pm 3$ )	30 ( $\pm 5$ )	60 ( $\pm 10$ ) )	90 ( $\pm 10$ ) )	120 ( $\pm 10$ ) )	150 ( $\pm 10$ ) )	180 ( $\pm 10$ )	210 ( $\pm 10$ ) )		
Informed Consent	✓											
Inclusion/Exclusion Criteria	✓											
General Medical History/Demographics	✓											
Physical Exam	✓		✓	✓	✓	✓	✓	✓	✓		✓	✓
Vital Signs §	✓		✓	✓	✓	✓	✓	✓	✓		✓	✓
mRS	✓		✓	✓	✓	✓	✓	✓	✓		✓	
NIHSS	✓		✓	✓	✓	✓	✓	✓	✓		✓	✓
SS-QOL	✓			✓					✓		✓	✓
Urine pregnancy test †	✓	✓ †	✓	✓	✓	✓	✓	✓	✓		✓	
12-lead ECG	✓		✓	✓	✓	✓	✓	✓	✓		✓	✓
Clinical Lab Evaluation*	✓ **			✓		✓			✓		✓	✓
PT/INR ( Warfarin arm only)		✓	✓	✓	✓	✓	✓	✓	✓		✓	✓
TEE	✓ †											
Event Monitor (prior to DC)		✓										
Carotid Ultrasound	✓											
MRI or CT scan	✓		✓						✓		✓	
Record AE/SAEs		✓	✓	✓	✓	✓	✓	✓	✓	✓	✓	✓
Prior and con. medications/procedures	✓	✓	✓	✓	✓	✓	✓	✓	✓	✓	✓	
Dispense Study Drug		✓	✓	✓	✓	✓	✓	✓				✓
Drug Compliance			✓	✓	✓	✓	✓	✓	✓		✓	✓
Non-study anticoagulation initiation									✓		✓	

$\beta$  drug initiation will be as follows: TIA: Apixaban arm day 0-3/Warfarin arm day 7( $\pm 5$ ): Small stroke: Apixaban arm day 3-5/Warfarin arm day 14( $\pm 5$ ): Medium stroke: Apixaban arm day 7-9/Warfarin arm day 14( $\pm 5$ )

\* Results of existing tests will be obtained from subject's hospital chart to assess eligibility. If tests results are not available labs will be performed at the visit. See section 6 for a detailed description of what this entails.

§ Vitals: BP, HR,, weight, (RR and Temperature are optional, height obtained at baseline only)

\*\* Labs for inclusion/exclusion criteria will include CMP, CBC with diff and platelets, Creatinine, PT/INR, LFTs and Lipid panel.

† performed prior to discharge

† All WOCBP MUST have a negative pregnancy test within 24 hours before receiving apixaban. The minimum sensitivity of the pregnancy test must be 25 IU/L or equivalent units of HCG. If the pregnancy test is positive, the subject must not receive apixaban and must not be enrolled in the study. † Study day at screening is day of event

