### 1.3 Name and Description of Investigational Product or Description of Intervention

Apixaban, a factor Xa (FXa) inhibitor, is chemically described as 1-(4-methoxyphenyl)-7-oxo-6-[4-(2-oxopiperidin-1-yl)phenyl]-4,5,6,7-tetrahydro-1H-pyrazolo[3,4-c]pyridine-3-carboxamide. Its molecular formula is C25H25N5O4, which corresponds to a molecular weight of 459.5. Apixaban has the following structural formula:

Apixaban is a white to pale-yellow powder. At physiological pH (1.2–6.8), apixaban does not ionize; its aqueous solubility across the physiological pH range is ~0.04 mg/mL.

This study is an open label, randomized, active controlled pilot study of Apixaban in subjects with NVAf who have, within 48 hours from signs and symptoms, been diagnosed with a TIA or a Small to Medium Ischemic Stroke as defined by the SACCO (see section 2.3).

In this study 120 patients with NVAf who have had a recent small or medium stroke or TIA (within 0-48 hours) will receive Apixaban twice a day for 180 days with drug initiation day 0-3 (TIA), day 3-5 (small stroke) or day 7-9 (medium stroke) respectively or receive standard of care warfarin starting at day 7±5 (TIA) or day 14 ±5 (small to medium ischemic stroke).

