### **5.8 Concomitant Medication**

Concomitant medication documentation will begin as soon as the subject takes the first dose of study medication. All concomitant medications used through the end of the study will be recorded. The dates of administration, dosage, and reason for use will be included. Subjects will be allowed to continue on concomitant medications. Any study related side effect (e.g., nausea) requiring medication management must be approved by the investigator prior to consumption.

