## **6 STUDY PROCEDURES**

### **6.1 Visit 1 Screening Visit/Baseline/Randomization (can occur on same day)**

- Signing an informed consent form prior to any study related activities
- Confirmation of Atrial Fibrillation either at admission or in subjects medical history
- Physical exam including vitals
- Body weight and height
- Review MRI results to determine diagnosis of TIA or determine size of Ischemic stroke
- Review of labs, echocardiogram, and EKG reports or draw labs and conduct EKG/ECHO if needed.
- Obtain medical history with demographics
- Schedule carotid ultrasound or CTA angiogram of the neck if not done at admission
- Schedule TEE if not done at admission (optional)
- Review of concomitant medications and procedures
- Obtain mRS, NIHSS and SS-QOL scales
- Urine pregnancy test (for women of childbearing potential)
- Review of all inclusion/exclusion criteria
- Treat any patient with hypertension according the current guidelines. (see section 5.2)

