**8.1.3 Safety Analysis/Secondary Aim**

The outcome will be measured at 30 and 180 days for all 6 subgroups: all coded as 0 or 1 at both follow-up points.

The analysis plan for this aim is very similar to that for the Primary Aim except the outcome here is defined as intracranial hemorrhage (which is coded as a 0 and 1 variable), and (2) the hypotheses for the outcomes are directional and therefore one-sided tests will be performed. AE incidence will be summarized along with the corresponding 95% confidence intervals.

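### Non-serious AE recording starts at first dose, which the design places later in the warfarin arm, so AE incidence is summarised over unequal windows

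*Combined protocol and SAP*

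**What the plan says.** Section 10.5.4 ties non-serious AEs to dosing: "The collection of non-serious adverse event (NSAE) information should begin at initiation of study drug". It then adds: "Nonserious adverse event information should also be collected from the start of a placebo lead-in period or other observational period", where the period meant is one that serves to establish baseline status.

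First dose depends on arm and stratum. For apixaban, section 1.3 gives "drug initiation day 0-3 (TIA), day 3-5 (small stroke) or day 7-9 (medium stroke) respectively". For warfarin, the same section and Table 2 give day 7±5 for TIA and day 14±5 for small and medium stroke. A footnote to the schedule counts study days from the index event. Section 5.2 places randomisation within 48 hours of symptoms, and section 4.1 follows all subjects for 180 days from screening.

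Other data start on a common clock. Section 10.4.1 says: "Following the subject’s written consent to participate in the study, all SAEs, whether related or not related to study drug, must be collected". Section 7.1 counts endpoint data from randomisation.

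The only planned AE analysis is one sentence in section 8.1.3: "AE incidence will be summarized along with the corresponding 95% confidence intervals". It names no start point and no exposure adjustment.

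For other treatments, section 5.8 says: "Concomitant medication documentation will begin as soon as the subject takes the first dose of study medication". Section 6.1 lists this at visit 1: "Review of concomitant medications and procedures". Section 6.3 asks about changes at drug initiation, and the schedule ticks prior and concomitant medications from visit 1 onwards.

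**The concern.** The trial compares two regimens that differ in start time as well as in drug, so the wait for warfarin is part of the comparator. If recording begins when the drug begins, the length of observation depends on the assigned arm. The unrecorded stretch also falls in the first days after the stroke or TIA, when event rates may differ from later ones. Two arms with the same true rate of non-serious AEs would then show different recorded incidences, with the lower one in the warfarin arm. Bleeding that is neither major nor serious is not a listed endpoint, so it would reach the report mainly by this route.

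Section 5.8 matters for a related reason. Antithrombotics taken before first dose could help explain a difference between arms, so the rule for when they are recorded should be clear and the same for everyone.

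**Working it through.** The plan states no figure on this point, so there is nothing of its own to reproduce. The start days come from section 1.3 and Table 2.

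**1. Gap in first dose.** Midpoint gap = warfarin midpoint − apixaban midpoint. Smallest gap = earliest warfarin − latest apixaban. Largest gap = latest warfarin − earliest apixaban.

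| Stratum | Apixaban | Warfarin | Midpoint gap (days) | Smallest to largest (days) |
|---|---|---|---|---|
| TIA | 0-3 | 2-12 | 7 − 1.5 = 5.5 | 2 − 3 = −1 to 12 − 0 = 12 |
| Small stroke | 3-5 | 9-19 | 14 − 4 = 10 | 9 − 5 = 4 to 19 − 3 = 16 |
| Medium stroke | 7-9 | 9-19 | 14 − 8 = 6 | 9 − 9 = 0 to 19 − 7 = 12 |

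With equal strata the mean gap is (5.5 + 10 + 6)/3 = 7.2 days.

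**2. Recording window.** Window = 180 (or 30) − first-dose day, at midpoints. Shortfall = gap / apixaban window.

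| Stratum | To day 180, apixaban vs warfarin | Shortfall | To day 30, apixaban vs warfarin | Shortfall |
|---|---|---|---|---|
| TIA | 178.5 vs 173 | 5.5/178.5 = 3.1% | 28.5 vs 23 | 5.5/28.5 = 19% |
| Small stroke | 176 vs 166 | 10/176 = 5.7% | 26 vs 16 | 10/26 = 38% |
| Medium stroke | 172 vs 166 | 6/172 = 3.5% | 22 vs 16 | 6/22 = 27% |
| Equal strata | 175.5 vs 168.3 | 4.1% | 25.5 vs 18.3 | 28% |

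The day-30 columns matter only if AEs are summarised at day 30. Section 8.1.3 sets days 30 and 180 for intracranial haemorrhage and gives no time point for AEs.

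**3. What this does to incidence (illustration on assumed rates).** The documents give no AE rates. Suppose both arms have the same true 180-day incidence I, a hazard m times higher in the first 14 days, and no recovery of pre-dose events. Then λ = −ln(1 − I)/(166 + 14m). For a patient starting on day s, recorded incidence = 1 − exp{−λ[m·max(0, 14 − s) + 180 − max(14, s)]}. Averaging this over the three strata at midpoint start days gives:

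| m (assumed) | I = 20%: apixaban vs warfarin | I = 40% | I = 60% |
|---|---|---|---|
| 1 | 19.6 vs 18.8% | 39.2 vs 38.0% | 59.1 vs 57.5% |
| 3 | 18.8 vs 16.9% | 38.0 vs 34.6% | 57.5 vs 53.3% |
| 5 | 18.3 vs 15.5% | 37.0 vs 31.9% | 56.3 vs 49.7% |
| 10 | 17.3 vs 12.9% | 35.3 vs 27.0% | 54.1 vs 43.0% |

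With a constant hazard the spurious difference is 0.8 to 1.6 percentage points. It grows with early clustering, and warfarin is lower in every cell.

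**4. After the fix.** Randomisation within 48 hours puts the start at day 0-2 in both arms. Each arm is then observed for 178-180 days to day 180, and the gap by design is zero.

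**5. Concomitant medications.** Section 5.8 starts documentation at first dose. Section 6.1 and the schedule start it at visit 1, and section 6.3 asks again at drug initiation. These cannot all be the rule.

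**The case against.** The strongest reply is that little is lost.

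- Serious AEs run from consent and primary endpoints from randomisation. Intracranial bleeds are sought on scans at day 14 and end of study in both arms. All of this stands and limits the point to non-serious AEs.
- The day-14 (±3) visit assesses AEs in both arms, even where warfarin may start as late as day 19. Section 10.1 says AEs are monitored throughout the study, and section 5.7 asks for at least monthly AE calls to subjects who stop treatment early and cannot attend clinic. Some pre-dose events may therefore be recovered, but section 10.5.4 does not tell sites to record them.
- The observational-period sentence in section 10.5.4 could be read to cover the wait. It makes the text ambiguous. However, a wait for assigned treatment after randomisation does not clearly serve to establish baseline.
- Section 8.1.3 only summarises AE incidence, and its one-sided test is for intracranial haemorrhage. That is correct. Incidences with confidence intervals will still be read across arms.

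A reader might also infer four stronger things that the documents do not support:

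- **All warfarin events up to day 19 are lost, and undosed patients contribute nothing.** The common start for serious AEs and endpoints rules this out.
- **The acute phase is missing only for warfarin.** Apixaban patients with medium stroke also lose the days before day 7-9.
- **The schedule contradicts section 10.4.1 because "Record AE/SAEs" is first ticked at visit 2.** A tick marks when staff ask, not which events count, and the schedule places no visit between visits 1 and 2.
- **Antithrombotics used during the wait go unrecorded.** Sections 6.1 and 6.3 and the schedule ask about medications at both ends of the gap. The contradiction with section 5.8 is real, but an omission is not shown.

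**Conclusion.** The point holds for non-serious AEs. Followed as written, section 10.5.4 gives a recording window that depends on the assigned arm: about 3-6% shorter for warfarin to day 180 and 19-38% shorter to day 30. This tends to make warfarin look safer.

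These figures assume first doses at the window midpoints and no recovery of pre-dose events. The 5.5 to 10 days is a range of midpoint differences, not a bound, since individual gaps can run from −1 to 16 days. Larger distortions need early clustering of AEs, which is plausible, but its size cannot be taken from the documents.

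Over 180 days at a constant rate the effect is small. It deserves correction because it is systematic in direction, easy to remove, and hard to repair later if events were never recorded. Section 5.8 is a separate internal contradiction to reconcile.

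**What to change.** - **Section 10.5.4:** start non-serious AE recording at randomisation in both arms. Leave serious AEs from consent, as in section 10.4.1. Delete the observational-period sentence or say what it means in this trial.
- **Schedule:** add a note to the AE row that the first AE enquiry after visit 1, whether at drug initiation or at day 14, covers everything since randomisation.
- **Section 5.8:** start concomitant-medication recording at visit 1, in line with sections 6.1 and 6.3 and the schedule.
- **Section 8.1.3:** summarise AE incidence from randomisation over the same window in both arms, counting all randomised patients. Report on-drug AEs per person-time as a separate summary.

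The cost is a wording change and a few more AE entries before first dose. It adds no visits and leaves treatment timing unchanged.
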